#### **8.4 Reporting of Pregnancy and Lactation**

Although pregnancy and lactation are not considered adverse events, it is the responsibility of Investigators or their designees to report any pregnancy or lactation in a subject (spontaneously reported to them) that occurs during the trial.

Pregnancies and lactations that occur after the consent form is signed but before treatment enrollment must be reported by the Investigator if they cause the subject to be excluded from the trial, or are the result of a protocol-specified intervention, including but not limited to washout or discontinuation of usual therapy, diet, or a procedure.

Pregnancies and lactations that occur from the time of treatment enrollment through 120 days following cessation of Sponsor's products, or 30 days following cessation of treatment if the subject initiates new anticancer therapy, whichever is earlier, must be reported by the Investigator. All reported pregnancies must be followed to the completion/termination of the pregnancy. Pregnancy outcomes of spontaneous abortion, missed abortion, benign hydatidiform mole, blighted ovum, fetal death, intrauterine death, miscarriage, and stillbirth must be reported as serious adverse events. If the pregnancy continues to term, the outcome (health of infant) must also be reported.

Such events must be reported within one (1) working day of the Investigator becoming aware of the event.

#### **8.5 Events of Clinical Interest**

Selected non-serious and serious adverse events are also known as Events of Clinical Interest (ECI) and must be reported to the Sponsor.

For the time period beginning when the consent form is signed until treatment enrollment, any ECI, or follow up to an ECI, that occurs to any subject must be reported within 24 hours to the Sponsor if it causes the subject to be excluded from the trial, or is the result of a protocol-specified intervention, including but not limited to washout or discontinuation of usual therapy, diet, or a procedure.

For the time period beginning at treatment enrollment through 30 days following cessation of treatment, any ECI, or follow up to an ECI, whether or not related to the Sponsor's products, must be reported within 24 hours to the Sponsor.

Events of clinical interest for this trial include:

1. Overdose of Sponsor's products, as defined in [Section 8.3 Definition of an Overdose for This Protocol and Reporting of Overdose](#), that is not associated with clinical symptoms or abnormal laboratory results
2. Elevated AST or ALT laboratory value that is greater than or equal to 3X the upper limit of normal and an elevated total bilirubin laboratory value  $\geq 2X$  the ULN and at the same time, an alkaline phosphatase laboratory value  $< 2X$  the ULN, as determined by way of protocol-specified laboratory testing or unscheduled laboratory testing. \*

**\*Note:** These criteria are based upon available regulatory guidance documents. The purpose of the criteria is to specify a threshold of abnormal hepatic tests that may require an additional evaluation for an underlying etiology.

All ECIs should be reported to the sponsor within 24 hours of the Investigator's knowledge of the event.

## 9.0 STATISTICAL ANALYSIS PLAN

### 9.1 Statistical Analysis Plan Summary

Key elements of the statistical analysis plan are summarized below.

#### 9.1.1 Hypothesis and Study Design

The study design is based on hypothesis testing of the ORR for pembrolizumab + Imprime PGG. For melanoma subjects, the null hypothesis is ORR  $\leq 5\%$ , versus the alternative hypothesis of ORR  $\geq 23\%$ ; for the TNBC subjects, the null hypothesis is ORR  $\leq 5\%$  (ORR=5% in KEYNOTE-086), and the alternative hypothesis is ORR  $\geq 21\%$ . Hypotheses testing will be conducted using a one-sided type I error of 0.05.

The study will incorporate Simon's optimal 2-stage design with sample size fixed at 12 subjects in Stage 1 (for melanoma, Simon's optimal 2-stage design has 12 subjects at Stage 1; for TNBC, a modified Simon's 2-stage design with the sample size fixed at 12 at Stage 1 is used). The safety criterion of  $\leq 4$  (or  $\leq 33\%$ ) subjects with Grade 3/4 adverse events in Cycle 1 within either tumor type must be met in order to proceed to Stage 2. The starting dose is 4 mg/kg for Imprime PGG. In the event there are a total of  $> 4$  (or  $> 33\%$ ) of subjects with Grade 3/4 adverse events in Cycle 1, the dose of Imprime PGG will be reduced to 2 mg/kg, and Stage 1 will be repeated at a dose of 2 mg/kg with an additional cohort of n=12 subjects. For the dose that meets the safety criterion in Stage 1, at least 1 response in

melanoma subjects and 1 response in TNBC subjects amongst the 12 subjects within each tumor type must be observed in order to proceed to Stage 2. The probabilities of early termination at Stage 1 for not achieving such responses are 0.54 and 0.54 if the null hypothesis is observed for melanoma and TNBC subjects, respectively. Stage 2 will enroll an additional 17 subjects with melanoma and 29 subjects with TNBC.

For the dose that meets the safety criterion in Stage 1, rejection of the null hypothesis will require documenting at least 4 objective responses among the total of up to 29 subjects with melanoma and 5 objective responses among the total of up to 41 subjects with TNBC.

The above designs correspond to a type I error 0.05 and power of 90% for both melanoma and TNBC. The PASS 14 Power Analysis and Sample Size System statistical software was used for the study design calculation.

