## 2.2 Trial Diagram

\* ≤ 4 subjects or 33% of Stage 1 subjects does not include infusion reactions (from either study drug) which were subsequently controlled and reduced in Cycle 1 via ameliorating actions, and which did not recur in Cycle 2

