## **3. Dose Reduction**

If a subject experiences an infusion reaction despite having been administered premedication and despite the infusion time being lengthened, the PI may re-challenge the subject at the next visit by dose reducing the Imprime PGG to 2 mg/kg.

All attempts should be made to ameliorate Grade 3/4 infusion reactions by the Investigator following the 3 recommendations provided above sequentially.

In Stage 1, any Grade 3/4 infusion reactions mitigated by these actions and either resolving or decreasing to Grade 1/2, if this mitigation occurs within Cycle 1 and the Grade 3/4 infusion reaction does not recur in Cycle 2, will not be counted towards the total of > 4 or 33% of Grade 3/4 adverse events which require halting the study in Stage 1 for each individual indication. Only Cycle 1 Grade 3/4 infusion reactions (or those which recur in Cycle 2) will be counted towards the total which would halt advancement to Stage 2.

- In the event there are a total of > 4 or 33% of Grade 3/4 adverse events in Stage 1 which were unable to be ameliorated by the sequential recommendations above, the dose of Imprime PGG will be reduced to 2 mg/kg.
- Stage 1 will be repeated with an additional cohort of n=12 subjects at the reduced dose of 2 mg/kg. Toxicity at the dose of 2 mg/kg will be assessed in this additional Stage 1 cohort in the same manner as was done for the initial dose of 4 mg/kg, with the identical sequential recommendations for any observed infusion reactions.
- Advancement to Stage 2 will be halted if there are > 4 or 33% of Grade 3/4 adverse reactions. Otherwise, subjects will proceed to Stage 2 with all subjects at the new, reduced dose of 2 mg/kg.

Note that continuation onto Stage 2 requires a demonstration of at least 1 or 2 objective responses in subjects with melanoma or TNBC, respectively, in addition to meeting the adverse event requirements detailed above, at either Imprime PGG dose of 4 mg/kg or 2 mg/kg. Please refer to the [Trial Diagram](#) in [Section 2.2](#) for a schema of the study flow from start to end.

In general, any Grade 4 non-infusion or non-hematological AE will lead to the withdrawal of the subject from treatment. A dosing delay of up to 3 weeks is allowed in case of Grade 3 non-hematological AEs to reduce toxicity to baseline or Grade 0-1. Dose levels will be adjusted individually for each study drug.

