Grades 3 or 4  Grade 3: Prolonged (ie, not rapidly responsive to symptomatic medication and/or brief interruption of infusion); recurrence of symptoms following initial improvement; hospitalization indicated for other clinical sequelae (eg, renal impairment, pulmonary infiltrates)  Grade 4: Life-threatening; pressor or ventilatory support indicated	
Stop Infusion.            Additional appropriate medical therapy may include but is not limited to:
 
 
Epinephrines**
 
IV fluids
 
Antihistamines
 
NSAIDS
 
Acetaminophen
 
Narcotics
 
Oxygen
 
Pressors
 
Corticosteroids
 
 
Increase monitoring of vital signs as medically indicated until the subject is deemed medically stable in the opinion of the Investigator.            Hospitalization may be indicated.            **In cases of anaphylaxis, epinephrine should be used immediately.  Subject is permanently discontinued from further study drug treatment.
	No subsequent dosing

Appropriate resuscitation equipment should be available at the bedside and a physician readily available during the period of drug administration.

For further information, refer to the Common Terminology Criteria for Adverse Events v4.03 (CTCAE) at <http://ctep.cancer.gov>

In Stage 1, any Grade 3/4 infusion reactions mitigated by these actions and either resolving or decreasing to Grade 1/2, if this mitigation occurs within Cycle 1 and the Grade 3/4 infusion reaction does not recur in Cycle 2, will not be counted towards the total of > 4 or 33% of Grade 3/4 adverse events which require halting the study in Stage 1 for each individual indication. Only Cycle 1 Grade 3/4 infusion reactions not controlled by the above measures (or those which recur in Cycle 2) will be counted towards the total which would halt advancement to Stage 2.

Dose will be managed individually for each study drug.

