## **8.0 ADVERSE EVENTS (SERIOUS AND NON-SERIOUS)**

### **8.1 Non-serious Adverse Events**

#### **8.1.1 Definition of Adverse Event and Non-serious Adverse Event**

The following definition of adverse event will be used for the study:

Any untoward medical occurrence in a study subject administered a pharmaceutical product and which does not necessarily have to have a causal relationship with this treatment. An adverse event can therefore be any unfavorable and unintended sign (including an abnormal laboratory finding), symptom, or disease temporally associated with the use of a medicinal (investigational) product, whether or not related to medicinal (investigational) product.

This definition includes any abnormalities or anomalies that were not seen at baseline or which worsened during the course of the study, if present at baseline. Disease progression, and events caused by disease progression, will be considered an efficacy endpoint and should not be reported as an AE, even if the event results in hospitalization. Therefore progression of the cancer under study is not considered an adverse event.

A “non-serious” AE is any event that does not meet the definition of “serious adverse event” (SAE) as presented in [Section 8.2](#) below.

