  - Yes – The time course between the administration of study drug and the occurrence or worsening of the AE is consistent with a causal relationship and no other cause (concomitant drugs, therapies, complications, etc.) can be identified
- Severity

The severity of all AEs should be graded according to the CTCAE v4.03. These criteria can be found at <http://ctep.cancer.gov/reporting/ctc.html>. For those AEs not listed in the CTCAE, the following grading system should be employed:

- Mild (CTCAE Grade 1): Transient symptoms, awareness of sign/symptom, but easily tolerated and no interference with subject's daily activities
- Moderate (CTCAE Grade 2): Marked signs/symptoms that interfere with subject's usual activities, but still acceptable
- Severe (CTCAE Grade 3): Incapacitating signs/symptoms which cause considerable interference with the subject's daily activities, unacceptable

- Life-threatening (CTCAE Grade 4): Life-threatening or disabling adverse event
- Death (CTCAE Grade 5): Death-related adverse event. See CTCAE Guidelines for assigning Grade 5.

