### 8.2.2 Reporting and Treating Serious Adverse Events

An AE that is serious (SAE) requires additional detailed reports and follow-up. The content of these detailed reports must address the Investigator's estimate of causality and must provide the information specified in the SAE Report Form and International Conference on Harmonisation (ICH) guidelines, in so far as is possible.

For the time period beginning when the consent form is signed until treatment enrollment, any serious adverse event, or follow up to a serious adverse event, including death due to any cause other than progression of the cancer under study, that occurs to any subject must be reported within 24 hours to the Sponsor if it causes the subject to be excluded from the trial, or is the result of a protocol-specified intervention, including but not limited to discontinuation of usual therapy, diet, or a procedure.

For the time period beginning at treatment enrollment through 90 days following cessation of treatment, or 30 days following cessation of treatment if the subject initiates new anticancer therapy, whichever is earlier, any serious adverse event, or follow up to a serious adverse event, including death due to any cause other than progression of the cancer under study, whether or not related to the Sponsor's products, must be reported within 24 hours to the Sponsor.

Additionally, any serious adverse event, considered by an Investigator who is a qualified physician to be related to the Sponsor's products that is brought to the attention of the Investigator at any time following consent through the end of the specified safety follow-up period specified in the paragraph above, or at any time outside of the time period specified in the previous paragraph, also must be reported immediately to the Sponsor.

All subjects with serious adverse events must be followed up for outcome.

Following is the safety contact information for reporting serious adverse events worldwide:

Safety Contact Information  
SAE [contact]  
[contact]  
E-mail: [[contact]](mailto:[contact])

The Investigator will be requested to supply detailed information regarding the event. All serious and unexpected AEs/SAEs must also be reported to the reviewing IEC/IRB as per specific requirements and a copy of that report must be retained at the investigative site and filed in the Investigator Site File.

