4 STUDY DESIGN

This is a Phase 2 study of Imprime PGG and pembrolizumab in subjects with advanced melanoma failing front-line treatment with checkpoint inhibitors or TNBC failing front-line chemotherapy for metastatic disease.

The study design is based on hypothesis testing of the ORR for pembrolizumab + Imprime PGG. For melanoma subjects, the null hypothesis is $ORR \leq 5\%$, versus the alternative hypothesis of $ORR \geq 23\%$; for the TNBC subjects, the null hypothesis is $ORR \leq 5\%$ ($ORR=5\%$ in KEYNOTE-086), and the alternative hypothesis is $ORR \geq 21\%$. Hypotheses testing will be conducted using a one-sided type I error of 0.05.

The study will incorporate Simon's optimal 2-stage design with sample size fixed at 12 subjects each in Stage 1 for advanced melanoma and for TNBC subjects. The safety criterion of ≤ 4 (or $\leq 33\%$) subjects with Grade 3/4 adverse events in Cycle 1 within either tumor type must be met in order to proceed to Stage 2 (Grade 3/4 infusion reactions which occur during Cycle 1 that either resolve or decrease to Grade 1/2 and recur in Cycle 2, will not be counted towards the total of ≥ 4). The starting dose is 4 mg/kg for Imprime PGG. In the event there are a total of > 4 (or $> 33\%$) of subjects with Grade 3/4 adverse events in Cycle 1, the dose of Imprime PGG will be reduced to 2 mg/kg, and Stage 1 will be repeated at a dose of 2 mg/kg with an additional cohort of $n=12$ subjects. For the dose that meets the safety criterion in Stage 1, at least 1 response in melanoma subjects and 1 response in TNBC subjects amongst the 12 subjects within each tumor type must be observed in order to proceed to Stage 2. Stage 2 will enroll an additional 17 subjects with melanoma, and 29 subjects with TNBC. For the dose that meets the Stage 1 safety criterion, success will be declared if at least 4 amongst the total of up to 29 subjects with melanoma, and 5 amongst the total of up to 41 subjects with TNBC achieve an objective response. The above design corresponds to a type I error 0.05 and power of 90% for both melanoma and TNBC.

The dosing schedule and the study assessments are presented in the schedule of assessment in the protocol.

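### The Stage 1 safety gate counts only Grade 3/4 events, so a subject whose only severe Cycle 1 event is a non-progression death (Grade 5) adds nothing to the count (minor)

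*Protocol*

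**What the plan says.** The gate appears in five readable places, all in terms of Grade 3/4.

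- Protocol 9.1.1, and 2.1 in the same words: 4 or fewer "subjects with Grade 3/4 adverse events in Cycle 1 within either tumor type must be met in order to proceed to Stage 2".
- Protocol 5.2.1.2.1, for the repeat cohort at 2 mg/kg: "Advancement to Stage 2 will be halted if there are > 4 or 33% of Grade 3/4 adverse reactions".
- Protocol 5.2.1.2.2, on which infusion reactions are not "counted towards the total of > 4 or 33% of Grade 3/4 adverse events which require halting the study".
- SAP 4: 4 or fewer "subjects with Grade 3/4 adverse events in Cycle 1 within either tumor type must be met".

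The body of the diagram in Protocol 2.2 cannot be read in the text available. Its footnote names no grade and only removes controlled infusion reactions: the limit of 4 "subjects or 33% of Stage 1 subjects does not include infusion reactions (from either study drug").

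Two other provisions define the gap. The severity scale in Protocol 8.1.2 has a separate fifth level, "Death (CTCAE Grade 5): Death-related adverse event". Protocol 8.1.1 states that "progression of the cancer under study is not considered an adverse event", so deaths from progression are outside adverse event reporting altogether. Deaths from other causes are inside it: Protocol 8.2.2 requires 24-hour reporting of serious events including "death due to any cause other than progression of the cancer under study, whether or not related" to the study products.

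**The concern.** The gate is the only numerical safety rule in the readable text. If more than 4 of 12 subjects count at 4 mg/kg, Imprime PGG is reduced to 2 mg/kg and Stage 1 is repeated with 12 more subjects. If more than 4 of 12 count at 2 mg/kg, advancement to Stage 2 stops. The count has no relatedness condition, so an unrelated Grade 3 event adds one. As worded, a death from a cause other than progression, with no other countable event, adds nothing. A toxicity rule that gives the worst outcome less weight than a Grade 3 event is hard to defend, and it could let a cohort pass at a dose that the rule is meant to reduce.

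Grade 3/4 cannot safely be taken as shorthand for Grade 3 and above. Protocol 9.1.6 uses the inclusive form (Grade 3 or higher) for the adverse event summary at the same interim, and the overview table in SAP 12.2 lists Grade III/IV events and fatal serious events as separate items.

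**Working it through.** **Inputs.** Cohort size 12 and limit 4 come from Protocol 9.1.1. The plan's only figure for the gate is the percentage: 4/12 = 33.3%, which agrees with the stated 33%. The plan gives no pass probability for the gate and no expected toxicity rates, so the rates below are assumptions.

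**Direct example.** Take 4 subjects with a countable Grade 3/4 event and 1 subject with a Grade 5 event only.

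- As written: 4/12 = 33.3%, criterion met.
- Counting Grades 3 to 5: 5/12 = 41.7%, criterion failed.

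**How often the wording would decide the outcome.** Let p be the probability that a subject has a countable Cycle 1 Grade 3/4 event, and q the probability of a Cycle 1 Grade 5 event without one. The two are mutually exclusive. Adding Grade 5 can only raise the count, so

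P(decision changes) = P(X ≤ 4; n = 12, p) − P(X ≤ 4; n = 12, p + q), with X binomial.

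Differences were taken before rounding.

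| p | Pass as written | Pass with Grade 5 counted, q = 0.5% / 1% / 2% | Change, q = 0.5% / 1% / 2% |
|---|---|---|---|
| 10% | 0.9957 | 0.9946 / 0.9935 / 0.9905 | 0.001 / 0.002 / 0.005 |
| 20% | 0.9274 | 0.9206 / 0.9134 / 0.8979 | 0.007 / 0.014 / 0.030 |
| 30% | 0.7237 | 0.7103 / 0.6968 / 0.6692 | 0.013 / 0.027 / 0.054 |

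The chance of at least one Grade 5-only subject among 12 is 1 − (1 − q)^12 = 0.058, 0.114 and 0.215 for q = 0.5%, 1% and 2%.

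**Given exactly one such death.** The decision changes only if exactly 4 of the other 11 subjects count: C(11,4) × p^4 × (1 − p)^7, with C(11,4) = 330 and p now the rate among those 11. This gives 0.016, 0.111 and 0.220 for p = 10%, 20% and 30%.

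**Efficacy design.** The exact two-stage calculation reproduces the stated figures. Early termination under the null is 0.95^12 = 0.540 in both cohorts. One-sided type I error is 0.0500 (melanoma) and 0.0452 (TNBC), and power is 0.902 and 0.906. None of these depends on which grades the safety gate counts.

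**The case against.** The strongest reply is that this is a choice of wording and that deaths are handled elsewhere at the same decision point. Non-progression deaths are reported within 24 hours (Protocol 8.2.2). Events of Grade 3 or higher, which include Grade 5, are summarized at the interim (9.1.6). The sponsor may halt for unacceptable risk (5.10). SAP 5.1 says that the Stage 1 decision considered adverse events including Grade 3/4, so it was not confined to the count. The gate is a necessary condition for Stage 2 and does not oblige anyone to proceed after a death. All of this stands. It shows that a death would be seen, but it does not put the death into the count that makes action mandatory.

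Reporting is also better than SAP 12.5 alone suggests. That section sorts deaths by 30 days from last dose, but SAP 12.2 and 12.3 add a count of fatal serious events, tables by maximum grade and a fatal-event listing. These are not broken down by Cycle 1. With 12 subjects per cohort, though, the count is easily made from them.

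Three further limits hold. SAP 5.1 describes the interim in the past tense, so the rule may not be used again. The unreadable diagram could conceivably carry different wording. The five-level list in 8.1.2 is introduced for events not listed in CTCAE. However, its levels carry the CTCAE grade labels and its last entry refers to the CTCAE guidelines for assigning Grade 5, so death is a separate grade either way.

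A reader might infer that the plan ignores deaths, that a death was missed in Stage 1, or that the Stage 1 decision was wrong. The documents support none of these. They provide several routes by which a death is reviewed, and they report no Stage 1 counts.

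**Conclusion.** The point holds as a minor flaw in the stated rule. In all readable text, a Cycle 1 non-progression death, related or not, with no separate countable Grade 3/4 event, is outside the Stage 1 count. A subject who dies after a separately recorded countable Grade 3/4 event in Cycle 1 is already counted, and progression deaths are not adverse events under this Protocol.

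Under the assumed rates, most of the change probabilities are below 3%. The largest, 0.054, needs 30% Grade 3/4 and 2% Grade 5 only within one three-week cycle. If such a death has occurred, however, the wording decides the outcome with probability up to 0.220 over the same range of Grade 3/4 rates.

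**What to change.** 1. **Report the completed Stage 1.** For each tumor type, give the number of subjects with a countable Cycle 1 Grade 3/4 event, the number with a Cycle 1 Grade 5 event and no countable Grade 3/4 event, and whether 4 or fewer of 12 still holds when the two are added. Say that the decision was made under the Grade 3/4 wording. Define countable by the Protocol exception (5.2.1.2.1 and 5.2.1.2.2): Grade 3/4 infusion reactions mitigated within Cycle 1 that do not recur in Cycle 2 are left out, and the limit is crossed at more than 4. SAP 4 cannot be used for this. It excludes reactions that do recur in Cycle 2 and refers to a total of 4 or more.

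2. **For any further use of the gate,** such as a repeat of Stage 1 at 2 mg/kg, reword it as Grade 3 or higher (Grades 3 to 5) in Protocol 2.1, 5.2.1.2.1, 5.2.1.2.2 and 9.1.1 and in SAP 4. Limit the infusion-reaction exception to Grade 3/4 reactions as the Protocol words it, correct SAP 4 to match, and check the diagram in Protocol 2.2.

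The cost is one reporting sentence per tumor type, edits to five passages and a check of one figure. No added data or subjects are needed.
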